	
To provide a preliminary assessment of the prognostic value of CTC data (positivity and gene expression) in predicting post-RP PCa metastasis development, overall survival and cancer specific survival.
 
To provide evidence and data which can be used to design a future clinical trial of a CTC- based intervention to be used to guide therapeutic choice in the management of high-risk localised PCa.
 
To evaluate the longer-term prognostic value of CTC detection and CTC gene expression for metastases and cancer-specific survival.
 
Primary endpoint
 
The primary outcome is post-RP treatment failure during the first 4.5 years of follow up from start of recruitment.
 
Post-RP treatment failure is defined as a PSA $\geq 0.2\text{mg/ml}$ at the routine PSA test 3 months after RP (commonly called 'failure to nadir') and remaining at this level or further increase afterwards without further treatment, or imaging detected appearance of cancer lesions.
 
Cancer lesions detected by imaging without a PSA rise might include neuroendocrine PCa and lesions detected by PSAM-PET. This combined post-RP treatment failure primary endpoint will maximally capture all the clinically significant cancer appearance events.
 
Secondary endpoints
 
BCR during the first 4.5 years of follow up: PSA $\geq 0.2\text{ng/ml}$ at any time post-RP and remaining at this level or further increase afterwards without further treatment.
 
Metastasis (any location)-free survival during the first 4.5 years of follow up. Only 5% of subjects with distant metastasis event (based on traditional imaging technologies) within this time frame (4-6).
 
Metastasis (any location)-free survival at 10 years follow up. to confirm that metastatic event rates have increased among the positives, i.e. a declining rate of "false positives".
 
Deaths from any cause during the first 4.5 years of follow up
 
Overall survival at 10 years of follow up.
 
Prostate cancer specific deaths during the first 4.5 years of follow up. Expected to be 2% or less based on previous studies in the post RP context.
 
Prostate cancer specific survival at 10 years of follow up. Our hypothesis is that most if not all of the patients dying of PCa will be in the CTC positive group.

Target sample size	294

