With an anticipated drop out of 40% due to either use of neo-adjuvant ADT or failure to consent in patients sent the PIS, we further anticipate 294 patients will contribute blood samples prior to RP. There is a target of 200 blood samples from eligible participants, who subsequent to having had RP do not have a positive surgery margin or other evidence of locally remaining disease, and do not subsequently have ADT (adjuvant ADT) or radiotherapy. It is intended that recruitment will continue until this target has been met.

6. Patient recruitment, sample collection, lab CTC analysis and follow-up procedures

Patients will be recruited (months 1-24) at UCLH, where the UK largest urological surgery centre is located and performs robot-assisted RP on PCa patients referred from several regional hospitals. The clinical team at UCLH will identify eligible patients who will be approached by the clinical research fellow (CRF) employed on the research project or the clinical care team for informed consent using the consent forms specifically designed for this project for blood collection and future research. Non-metastatic disease will be based on the current standard diagnostic imaging methods including CT/MRI and PSMA-PET/bone scan. A pre-surgery PSA test will be performed routinely at UCLH.

2 x 10 ml blood samples will be collected (months 1-27) using the lavender cap EDTA tube according to our established method from each consented patient by the CRF or the clinical care team at UCLH during the pre- and post-RP PSA test blood sampling, and taken to the laboratory at Barts Cancer Institute, [name] either by the CRF, a tissue bank acquisition officer (TBAO)(in the absence of the CRF) or the postdoc (anonymise samples transfer in the absence of CRF and TBAO) under the signed material transfer agreement (MTA), at room temperature. The samples will be transported in

Protocol for spin off research project- Circulating tumour cells as biomarkers to predict prostate cancer metastasis for treatment stratification of localised cancer

designated sample carrier using a taxi service. No public transport is to be used for moving samples between sites.

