Each patient will be allocated a unique ID and will be used by the lab research team. This unique ID will be recorded in the tissue bank database for future correlation analysis of the CTC results with clinical follow-up data. Sample processing will be performed in tissue culture hood in the designated lab. The whole blood sample will be processed within 4hrs for CTC analysis after collection. Standard Operating Procedure (SOP) (C-ProMeta-1) that is generated describing sample process and analyses need to be followed. There will be fewer patients for the post-RP than the pre-surgery blood collection based on patient exclusion criteria after RP.

Based on the sample size calculation 200 patients will be recruited for both pre- and post-surgery blood sample collections for CTC analysis, which are expected to be achieved within the first two years of the project.

Patient informed consent (including the permission to conduct remote longer-term follow-up) and blood sample collection will be performed by the CRF or the clinical care team.

All patients will have a PSA test at 3 months after their RP during a routine follow-up at UCLH. A PSA ≥ 0.2 will be recorded as a treatment failure event and PSMA-PET scans will be performed as standard clinical care at the study hospitals to detect small PCa lesions. After 3 months, patients are referred back to their original referring centres. Patients with negative PSA results at three months will be followed up by telephone or online app by the study CRF in order to ascertain whether subsequent PSA tests are positive (PSA ≥ 0.2), indicating BCR, metastasis occurs as detected by cancer imaging including PSMA-PET scan or if they have received salvage treatment with hormones/radiotherapy. In addition, details of long term follow up, such as post-operative PSA results and record of adjuvant therapies, will be sourced from patients' hospital electronic medical records, or requested from their local GP or health centre. All patients will be followed-up until the end of the project for metastasis progression as detected by imaging, PCa-specific death and death from any causes. In addition to data collected within the 5-year funded period, we plan to conduct remote longer-term follow up with fully informed consent from patients at point of enrolment, including:

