will be reported alongside the number of these participants with a positive by CTC result, and positive combined CTC result. Metastases-free, PCa-specific and overall survival will be reported during the 5 years study time frame and it is intended to perform a later analysis at 10 years of follow up. Preliminary investigation of the prognostic value of pre-surgery CTC data in terms of predicting survival outcomes will be investigated using Cox regression, with hazard ratios reported with associated 95% CIs. CTC data will be explored alongside other pre-surgery risk factors such as plasma PSA using multivariate analysis. Recurrence events and follow up CTC results will be reported and compared over time. The above analyses will be applied to the CTC gene panel. The gene panel will also be correlated with the pre- and post- RP CTC number changes and cancer progression events.

CTC results will be presented for the whole cohort who provided analysable blood samples and stratified by those included in the above analyses, and those excluded due to reasons such as a positive surgery margin, other evidence of locally remaining disease, and who subsequently have adjuvant ADT or radiotherapy.

8. Ethics

The study is a spin out project of the parent project authorised under RLTB ethics, where the main research tissue bank approval provided by the London City & East Research Ethics Committee.

9. Data handling, storage and record keeping- to describe who and how the data will be handled, which data nodes will be used, where it will be stored and security of the data

The CRF (funded by QMUL, but with contract at UCLH) will be part of the study management group and will act as the contact point between UCLH and QMUL. Under the MTA and data sharing agreement (DSA) between the two institutions and with patient consent, the CRF will collect blood samples during pre-surgery operation and after the surgery during the first PSA follow-up visit at UCLH.

The following clinical data will be collected for each patient by the CRF:

- Histology reports
- Clinical stage
- Prostate Specific Antigen (PAS) (pre- and post-surgery)
- Imaging (MRI, PSMA-PET/CT and bone scan)
- Results and record of adjuvant therapies
- Treatment date and method for post-surgery cancer recurrence

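### The undated exclusion for locally remaining disease overlaps the imaging limb of the primary endpoint, and the protocol does not say which rule prevails

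*Protocol*

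**What the plan says.** **The exclusion.** Section 5 (Study population) sets a target of 200 blood samples from men who after RP "do not have a positive surgery margin or other evidence of locally remaining disease". Section 7 (Statistical considerations, Method of analysis) confirms that this is an analysis exclusion. CTC results are to be shown for the whole cohort, split into the men analysed and "those excluded due to reasons such as a positive surgery margin, other evidence of locally remaining disease", among other reasons. The list of reasons is open. Neither section gives a time limit, a method (pathology, PSA or imaging) or an assessor.

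**The endpoint.** Table 1 in Section 3 defines post-RP treatment failure as a PSA at or above 0.2 at the three-month test that persists or rises, "or imaging detected appearance of cancer lesions". The imaging limb has no restriction by site. Section 7 states the primary analysis as sensitivity of the pre-surgery CTC result for failure at 4.5 years, with progression by any imaging included.

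**The link between them.** Section 6 says that a three-month PSA at or above 0.2 "will be recorded as a treatment failure event and PSMA-PET scans will be performed as standard clinical care", with the aim of finding small lesions.

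**The concern.** A PSMA-PET done after a raised three-month PSA can show a lesion in the prostate bed. That lesion is a cancer lesion on imaging, so it is a primary failure event. It is also, in ordinary language, evidence that disease remains locally after surgery, so it is a reason for exclusion. The two rules give opposite instructions for the same man.

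The choice is unlikely to be neutral. Sections 2.1 and 7 rest on the hypothesis that CTCs mark micro-metastasis. On that hypothesis, a man whose failure is purely local is the one most likely to have a negative CTC result, and so to count as a false negative. Dropping him because of a finding that is itself the outcome takes a probable false negative out of the sensitivity denominator. Sensitivity is the primary estimate, and it would then depend on which sentence the analyst follows.

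**Working it through.** **1. The plan's own figures.** Inputs from Section 7 (Sample size): expected sensitivity 0.95, precision ±0.05, 95% confidence interval, prevalence 40%, inflation 8.5%.

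- Events: 1.96² × 0.95 × 0.05 / 0.05² = 72.99, rounded up to 73.
- Men: 73 / 0.40 = 182.5, rounded up to 183.
- Inflated: 183 / (1 − 0.085) = 200.

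All three agree with the protocol, so the sample-size arithmetic is not at issue.

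**2. How many men the post-RP rules govern.** Section 5 expects 294 men to give blood before RP and 200 to remain. The difference is 94 men (94/294 = 32%). This covers all post-RP reasons together; the protocol does not split it.

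**3. The two rules side by side.**

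| Finding after RP | Excluded under Sections 5 and 7? | Failure under Table 1 and Section 6? |
|---|---|---|
| Positive margin on pathology | Yes | No, not by itself |
| Persisting PSA ≥ 0.2 at three months, no lesion located | Nothing says so | Yes |
| Prostate-bed lesion on post-RP imaging | Yes, read literally | Yes |
| Lesion outside the prostate bed | No | Yes |

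Only the third row is in conflict.

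**4. Effect on sensitivity (illustration).** Take 200 × 0.40 = 80 failures, of which *n* are local with CTC positivity *s*, and let the rest have the protocol's expected 95%. The protocol gives neither *n* nor *s*; both are assumed here and shown as ranges.

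Sensitivity with local failures counted = [(80 − n) × 0.95 + n × s] / 80. With them excluded it is 95%.

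| Local failures *n* | s = 25% | s = 50% | s = 75% |
|---|---|---|---|
| 8 (10%) | 88% | 90.5% | 93% |
| 16 (20%) | 81% | 86% | 91% |
| 24 (30%) | 74% | 81.5% | 89% |

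For example, with n = 16 and s = 50%: (64 × 0.95 + 16 × 0.5) / 80 = (60.8 + 8) / 80 = 86%.

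The gap from 95% runs from 2 to 21 points. It exceeds the planned precision of 5 points in six of the nine cells. If local failures were as often CTC-positive as the others (s = 95%), the gap would be zero.

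**The case against.** The best reply is that the exclusion was meant to be early and surgical. It is paired with margin status, and both phrases can be read as describing what the operation left behind. Section 6 supports this: "There will be fewer patients for the post-RP than the pre-surgery blood collection based on patient exclusion criteria after RP". Section 9 places that second sample at the first PSA visit after surgery. A rule that reduces the number of men giving the sample would be applied before that visit's PSA result exists, and so before any scan the result prompts. This is probably the intention. It remains an inference: no cut-off is written, margin status is already named separately, and the words about other evidence are not tied to the specimen.

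Section 7 also promises CTC results for the excluded men, so their CTC status would be visible. No accuracy estimate that includes them is promised.

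The endpoint table that Section 7 cites as Table 4 is not in the text at hand and might narrow the endpoint. The definition in Table 1 is complete as it stands and carries no site limit. Dating an analysis set can be left to a statistical analysis plan, but here the protocol itself states both rules, and they collide.

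Three stronger readings are tempting and are not supported:

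- **That a raised three-month PSA alone triggers the exclusion.** No section says so. Section 6 records it as failure without condition, and Section 2.1 takes recurrence after RP as a sign of micro-metastasis.
- **That the same man is entered both as excluded and as a failure.** The text shows only that two rules apply to him.
- **That the exclusion leaves fewer than the 73 required events.** Subtracting 8, 16 or 24 from 80 gives 72, 64 or 56, but this treats the 200 as fixed before exclusion. Section 5 counts the 200 after exclusion and continues recruitment until it is reached. On the same assumptions, 200 retained men give 72/192 × 200 = 75, 64/184 × 200 = 70 or 56/176 × 200 = 64 events. If the 40% prevalence already describes the retained men, there are 80 events and no shortfall.

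**Conclusion.** The point holds in a narrow form. For a man with a prostate-bed lesion on post-RP imaging, the protocol's exclusion and its primary endpoint conflict, and no section says which prevails. Applying the exclusion literally would condition the analysis set on the outcome and would probably bias sensitivity upward. The direction rests on the protocol's hypothesis about CTCs and micro-metastasis. The size rests on two assumptions without a source in the protocol, the share of failures that are local and their CTC positivity. Over the ranges used, sensitivity would be 74-93% with these men counted against 95% without them. The likely intention, an exclusion fixed by surgery and pathology, would remove the problem, so this is an ambiguity to close before outcomes are analysed and not a fundamental flaw in the design.

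**What to change.** In Section 5 and in the Method of analysis in Section 7, state that this analysis-set exclusion rests only on facts fixed by the RP operation and its pathology report, such as margin status and residual disease recorded at surgery. Add that any PSA or imaging finding at or after the three-month test is an outcome and never a reason for exclusion from the accuracy analysis. Sections 3, 5, 6 and 7 would then agree.

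The cost is about one sentence in each of two places. It needs no new data and does not touch patient care. The downside is that the estimated sensitivity may be less favourable. The change should be made before CTC results are linked to outcomes, because afterwards either reading could be chosen with the result in view.

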2.1. Rational: As many prostate cancer (PCa) cases diagnosed at early stage are indolent, PCa progression risk- stratification systems have been developed, based on biopsy characteristics, staging and PSA levels, and patients are classified into low- intermediate- and high-risk groups for treatment stratification. However, these systems are imperfect. Moreover, determining which curative treatment will be most effective for individual patients with localised PCa is challenging and remains a major obstacle in improving patient management and is recognised as an unmet clinical need. Cancer metastasis is the main cause of PCa death and determines the selection of therapeutic methods. Theoretically, localised PCa should be cured by radical prostatectomy (RP). However, more than half of apparently localised high-risk PCa cases treated by RP reoccur, indicating the presence of undetectable micro-metastasis at the time of surgery. These particular patients require additional treatment, usually with radiotherapy and systemic hormone therapy. The major challenge in managing aggressive localised PCa is differentiating truly localised PCa from those with micro-metastatic disease, which cannot be cured by RP. Pelvic lymph node dissection for high-risk localised disease is the current diagnostic test for assessing spread of disease but is invasive and performed during surgery. A test is required which can be performed before surgery to distinguish patients suitable for RP from those who would benefit from more extensive systemic treatment and radiotherapy. No current imaging test has the resolution to detect micro-metastases that may consist of just a few viable PCa cells. Circulating tumour cells (CTCs), the seeds of cancer metastasis, can occur at a very early stage of cancer development. We hypothesise that detection of CTCs provides an accurate indicator of cancer micro-metastasis and CTC gene expression may predict the potential of future metastasis development. We have established a promising CTC analysis method, by which we have detected CTCs in all patients with metastatic PCa and for the first time have demonstrated the value of using CTC analysis in predicting **clinically significant** post-biopsy **clinically significant** PCa outcome in pre-biopsy patients. Our CTC results may reflect the existence of micro-metastasis and predict PCa progression risk better than the current imperfect risk-stratification systems. Therefore, a prospective study with

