Study objectives and endpoints	
Objectives are set in the context of high-risk patients diagnosed with localised prostate cancer scheduled for robot-assisted RP who have not had neoadjuvant ADT, and are listed below.
 
Primary objectives:
 
To establish the value of CTC positivity in predicting post-RP treatment failure, including BCR and new lesions detected by cancer imaging.
 
To establish the value of a combined CTC test (including CTC enumeration and gene expression) in predicting post-RP treatment failure and the time of the development of BCR and new lesions detected by cancer imaging.
 
Secondary objectives
 
To investigate the potential of CTCs in predicting positive lymph node metastasis, which affects the selection and scale of RP as the initial treatment.
 
To assess potential for convenient non-invasive disease monitoring

Protocol for spin off research project- Circulating tumour cells as biomarkers to predict prostate cancer metastasis for treatment stratification of localised cancer

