Potential participants will be identified, approached and screened by the study team if they are interested in participating as described in the study design above. In order to recruit patients meeting the eligibility criteria, it will be necessary to screen all patients in the participating centre who are diagnosed with high risk localised PCa based on the current European Urology Association classification system who have been deemed eligible for radical prostatectomy by a specialist multi-disciplinary committee, and who have been scheduled for surgery to completely remove the cancer in the prostate gland.

Based on past patient numbers at UCLH, it is anticipated that approximately 600 patients will meet these initial criteria over the 2-year recruitment period. However, to meet our target

Protocol for spin off research project- Circulating tumour cells as biomarkers to predict prostate cancer metastasis for treatment stratification of localised cancer

recruitment we anticipate contacting approximately 490 of these potential participants (Figure 1). Potential participants will be identified via MDT meetings and in clinics. Potential participants who meet eligibility criteria will be posted, emailed or physically provided with a patient information sheet (PIS) approved by the ethics committee, prior to their next clinic appointment in order to give sufficient time to consider the information. At their clinical consultation (remote or face to face), they will be approached regarding the study, and given the opportunity to ask any questions and confirm eligibility checks. Inclusion and exclusion criteria are given below.

Inclusion criteria

- High/high intermediate risk non-metastatic PCa based on the EAU stratification system
- Scheduled for robot-assisted RP
- Informed consent

Exclusion criteria

- With other cooccurring cancers
- Neo-adjuvant ADT
- Adjuvant ADT

Withdrawal Criteria

- Unable or unwilling to undergo RP
- Patient changes their mind and withdraws their consent

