- **MRI score:** Multi-parametric MRI Likert scale 1-5 where >3 indicates aggressive cancer.
- **BCR:** PSA $\geq 0.2\text{ng/ml}$ at any time post-RP and remaining at this level or further increase afterwards without further treatment (see Table 4 for endpoint definitions)
- **Post-RP treatment failure:** (see Table 4 for endpoint definitions)

2). Sample size

The study hypothesis is that the presence of CTCs has close to 100% sensitivity and specificity for micro-metastasis, and thus RP treatment failure. Due to the long-term nature of recurrence events, there will be a proof of principle part to this study which occurs within the funded study timeframe of 5 years, and an intention to collect and analyse relevant longer-term events at 10 years (see section 4 for objectives and endpoints). The primary endpoint is **post-RP treatment failure**, the majority of which will be due to BCR. Despite the long-term nature of events of interest, it will be possible to provide a timely estimate of sensitivity, since of those who do have an observable BCR event, most if not all are expected to have a positive CTC result. Thus, consistent with previous work, this study estimates predicting post-RP cancer events with 95% sensitivity. During the first 4.5 years of follow up, the hypothesised prevalence of BCR events to be at least 40%.

In order to confirm an expected sensitivity of 95% within 5% precision either side of a 95% confidence interval (CI) in a sample with an underlying prevalence of 40%, requires at least 73 events, that is at least 183 recruited individuals. Inflate this by 8.5% to a target recruitment of 200 to ensure suitability of samples and measurable outcomes.

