The recruitment plan will be 200 patients in the first two years of the 5-year project to allow an approximate 3.5 to 4 year median follow up. Specificity is important considering the future circumstance of potentially denying patients curative surgery, if a CTC test indicates metastasis. A study size of 200 and 120 true negatives would give a 97.5% lower confidence limit on a specificity of 99% (1% false positive rate). However, it is anticipated the specificity will be low due to positive results for those who recur beyond the 5-year study. Assuming these events are due to micro-metastases at the time of surgery, observed sensitivity and specificity will be used, plus additional analyses assuming up to 20% of the events occur after the funded 5-year project⁴⁻¹¹ to estimate the real false positive and negative rates.

3). Method of analysis

Study flow and patient characteristics will be reported. Measures of accuracy will be presented with 95% confidence intervals (CIs). The primary analysis is the estimation of the sensitivity of the pre-surgery existence of CTCs for detection of RP treatment failure, i.e. BCR or progression detected by any imaging at the 4.5-year follow-up time point. Observed specificity, positive and negative prediction values will also be reported at 4.5 years of follow up, with a note to indicate that these estimates are subject to change given the long-term nature of recurrence events. Specificity will be presented over time and additional analysis accounting for artificial inflation of false positives based on increasing prevalence of events. BCR-free survival will be estimated and Kaplan-Meier curves presented.

The number of participants with recorded metastases, lymph node metastases, deaths from any cause and PCa deaths during the first 4.5 years of follow up

Protocol for spin off research project- Circulating tumour cells as biomarkers to predict prostate cancer metastasis for treatment stratification of localised cancer

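### The 4.5-year accuracy measures are confined to men selected on facts known only after surgery, and none is planned for the pre-surgery population that the objectives and the intended use concern

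*Protocol*

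**What the plan says.** **Population of the objectives.** Table 1 (Section 3) states: "Objectives are set in the context of high-risk patients diagnosed with localised prostate cancer scheduled for robot-assisted RP who have not had neoadjuvant ADT". Section 2.1 gives the purpose: "A test is required which can be performed before surgery to distinguish patients suitable for RP". The sample size text in Section 7 looks ahead to the same decision: "Specificity is important considering the future circumstance of potentially denying patients curative surgery, if a CTC test indicates metastasis".

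**Population of the analysis.** Section 5 expects 294 men to give blood before RP. It sets a target of 200 who after RP have no positive margin, no other sign of local disease, "and do not subsequently have ADT (adjuvant ADT) or radiotherapy". Method of analysis (Section 7) shows that this is more than a recruitment count, because it separates the men in the analyses from "those excluded due to reasons such as a positive surgery margin, other evidence of locally remaining disease, and who subsequently have adjuvant ADT or radiotherapy". Those analyses include the primary sensitivity at 4.5 years, with specificity and positive and negative predictive values.

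**Whole cohort.** The commitment is: "CTC results will be presented for the whole cohort who provided analysable blood samples and stratified by those included in the above analyses". The definitions in Section 7 treat a CTC result as the outcome of the test, not its agreement with later failure. Section 6 foresees accuracy analyses at 7.5 and 10 years but names no population for them.

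**The concern.** Margin status, residual local disease and adjuvant treatment are settled only after the decision the test is meant to inform. A man weighing RP cannot know whether he will fall into the analysed group. Accuracy conditional on that group answers a different question from the one set in Table 1. Predictive values are especially exposed, because they depend directly on the failure rate and case mix of the men analysed. Aim IV intends these data to support the design of a trial in which CTC results guide the choice of treatment, so a figure for the pre-surgery population is needed.

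A smaller difficulty lies in the wording of the exclusion. ADT is labelled adjuvant, but radiotherapy carries no qualifier or time limit. Neither it nor other evidence of local disease is ordered against failure. Read literally, a man who fails and then has radiotherapy, or whose failure is a local lesion seen on imaging, could be both an event and an exclusion.

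**Working it through.** **1. The plan's own figures reproduce.**
- Events for 95% sensitivity within ±5 points: 1.96² × 0.95 × 0.05 / 0.05² = 72.99, so 73.
- Men at 40% prevalence: 73 / 0.40 = 182.5, so 183.
- With the 8.5% allowance: 183 / 0.915 = 200.
- Sampled men: 490 × 0.60 = 294.

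**2. Men without a planned 4.5-year accuracy measure.** 294 − 200 = 94, and 94 / 294 = 32%. This is an upper limit. Section 5 withdraws men who are "Unable or unwilling to undergo RP" and those who withdraw consent, and it does not break down the fall from 294 to 200.

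**3. What could differ (illustration only; every input about the excluded men is assumed).** In the 200, expect 200 × 0.40 = 80 failures, of which 76 are detected at 95% sensitivity. With f failures among the excluded men who had RP and sensitivity s in them, sensitivity in all men who had RP is (76 + f × s) / (80 + f).

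| Excluded men who had RP | f at 40% failing | s = 95% | s = 70% | s = 50% |
|---|---|---|---|---|
| 47 | 18.8 | 95% | 90% | 86% |
| 94 | 37.6 | 95% | 87% | 81% |

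The table includes no change at all. The documents give no value for s, for the failure rate in these men, or for their number.

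**4. Precision of a whole-cohort estimate.** If all 294 had RP and 40% failed, there would be 117.6 failures. At 95% sensitivity the half-width is 1.96 × √(0.0475 / 117.6) = 3.9 points.

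**5. Ordering of treatment and failure.** Suppose a share r of failures were removed because of later treatment.
- *Without replacement:* 80 × (1 − r) falls below 73 once r exceeds 1 − 73/80 = 8.75%, about 9%. At r = 10%, 72 events remain and the half-width is 1.96 × √(0.0475 / 72) = 5.03 points.
- *With recruitment continued to 200, as Section 5 intends:* prevalence is 0.4(1 − r) / [0.6 + 0.4(1 − r)]. At r = 10% this is 0.36 / 0.96 = 37.5%, giving 75 events and ±4.9 points. Break-even is at prevalence 73/200 = 0.365, where 0.4(1 − r) = 0.6 × 0.365 / 0.635 = 0.345 and r is about 14%.
- *On the adjuvant-only reading:* r = 0 and nothing changes.

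**The case against.** **The restricted set is deliberate.** Section 7 describes a proof-of-principle stage and hypothesises that CTCs mark micro-metastasis. Leaving out men with known local residual disease fits that hypothesis, and the whole cohort's CTC results are shown openly by inclusion status. This stands, and is why the restricted set should remain primary. It does not supply accuracy in the population of Table 1.

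**The analysis plan may add it.** Many supplementary analyses are properly left there. Here, however, the protocol itself fixes the exclusion and says what the whole cohort will receive.

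**The stated sensitivity must be biased.** A reader might infer this, but the documents do not support it. Patients and treating clinicians are blinded to CTC results (Table 1), so CTC status cannot drive treatment directly. An indirect route, for example through extent of disease, is possible but not shown. The table in the working is arithmetic on assumed inputs.

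**Failures will be dropped and precision lost.** This too can be inferred from the unqualified mention of radiotherapy, but the surrounding text points the other way. Section 6 has the post-RP exclusions already reducing the 3-month blood collection. It records a 3-month PSA of 0.2 or more as a failure and lists salvage treatment as follow-up data. Adjuvant-only exclusion is the likely intent. What remains is a gap in wording.

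**The excluded men lack PSA data.** Section 6 ties telephone or app follow-up to men with a negative 3-month PSA. The same section also draws post-operative PSA from hospital and GP records and plans annual contact without that limit. The data therefore appear to be available.

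**Conclusion.** The point holds as one of applicability. The 4.5-year sensitivity, specificity and predictive values describe men selected after surgery. No such measure is planned for the men to whom the objectives and intended use refer. Up to 32% of sampled men are affected, on the protocol's figures of 294 and 200. The effect on the accuracy figures cannot be determined from the documents and may be nil. The restricted estimate remains valid for its own group.

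The ordering issue is secondary. On the likely reading the planned 73 events and ±5 points stand. On the literal reading they are at risk only if about 14% of failures are removed with recruitment refilled to 200, or about 9% without refilling; removals after recruitment closes could not be refilled. These thresholds assume 40% prevalence and that the 8.5% allowance ("Inflate this by 8.5% to a target recruitment of 200 to ensure suitability of samples and measurable outcomes") is not used up by other losses.

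**What to change.** 1. Keep the restricted set as the primary analysis and say that it serves the micro-metastasis hypothesis.
2. Prespecify a supplementary analysis of sensitivity, specificity, PPV and NPV at 4.5 years in all men with an analysable pre-RP sample who had RP. Show men treated before any failure counted all as failures and then all as non-failures. Name the population for the 7.5- and 10-year accuracy analyses.
3. Reconcile the exclusion wording in Sections 5, 6 and 7 with the endpoint wording in Table 1 and the Section 7 definitions, which also turns on further treatment. For the analysis set, state that a man who has already met the failure definition is counted as a failure, and is not excluded for later treatment or for the finding that defined the failure.

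**Cost.** A wording change and one more table, with no extra sampling. PSA capture for the excluded men should be confirmed. Sensitivity in the wider set will probably be lower, because it includes failures of local origin. The two-way range may be wide. As an assumed example, take 10, 20 or 30 such men among 294, half of them CTC-positive, with 40% failing and 95% sensitivity in the rest. Counting them all as failures gives (107.9 + 5) / 123.6 = 91%, (104.1 + 10) / 129.6 = 88% or (100.3 + 15) / 135.6 = 85%, against 95% when all are counted as non-failures.
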